8.8. Quality control

The data research partners that will contribute data for this study are all participants in the Sentinel System. The study will use the same data quality assurance (QA) procedures as the Sentinel System and the same curated data sets used by the FDA to conduct Sentinel analyses. The QA approach assesses consistency with the SCDM, evaluates adherence to data model requirements and definitions, evaluates logical relationships between data model tables, and reviews trends in medical and pharmacy services use within and across data research partners. Full QA processes and details on the Sentinel database curation approach are documented on the Sentinel website (Sentinel, 2017; Sentinel Initiative, 2021). The data curation approach is consistent with guidance set forth by the US FDA in its current recommendations for data QA, Guidance for Industry and FDA Staff: Best Practices for Conducting and Reporting Pharmacoepidemiologic Safety Studies Using Electronic Healthcare Data, Section IV.E Best Practices – Data Sources: Quality Assurance (QA) and Quality Control (QC), published in May 2013 (FDA, 2013; Sentinel, 2017). This Guidance describes best practices that particularly apply to observational studies designed to assess the risk associated with a drug exposure using electronic healthcare data.

In addition to QA of data elements, HPHCI adopts standard SAS programming QA and QC processes used by the Sentinel System to check SAS programs and deliverables. Figure 4 illustrates the standard operating procedures for SAS programming QA and QC in the Sentinel System.

Figure 4. Standard operating procedure for SAS programming quality assurance and quality control in the Sentinel System

QC = quality control.

8.9. Strengths and limitations of the research methods

A major strength of this study is that it will include a very sizeable source population in the US, as the participating data research partners together collect data on more than 100 million individuals. The use of secondary data will enable the efficient assessment of many safety events of interest identified by the CDC's VSD and the FDA's BEST Initiative, in addition to pregnancy safety outcomes, while using robust study design and analytic approaches to adjust for potential confounding. Moreover, the secondary use of administrative data collected as part of routine medical care avoids selection bias that might occur in primary data collection studies, as an individual's inclusion in this study is not voluntary.

Nevertheless, this study is subject to limitations arising from the use of secondary data and the selected study designs. Limitations related to the data sources include the potential for lack of recording in claims and electronic health records of COVID-19 vaccines administered without reimbursement from health insurers. If the data appear to be substantially incomplete in monitoring analyses, then the primary study design may be reconsidered. If this happens, the SCRI may be designated as the primary study designs, and/or linkage to immunization registries may be considered. Additionally, the use of data from claims and electronic health records may lead to some misclassification of outcomes (e.g., false positives and false negatives). Some events, such as spontaneous abortion, will be incompletely captured in existing databases. Conversely, validation studies of ICD-10-CM–based algorithms for many

PFIZER CONFIDENTIAL

CT24-WI-GL02-RF02 3.0 Non-Interventional Study Protocol Template For Secondary Data Collection Study 20-May-2021 Page 99 of 120 of the safety events of interest have been limited, and the accuracy of algorithms for many safety events of interest are unknown. When possible, validated algorithms will be used, and outcomes that are likely to be misclassified (based on prior validation studies and clinical expert input) may be validated through review of medical records or claims profiles, depending on the safety event of interest.

A study design-related limitation is that any uncertainty regarding risk periods will lead to misclassification and attenuation of risk estimates. Sensitivity analyses with alternative risk intervals will be considered for outcomes for which the risk interval is not well characterized.

A limitation of the cohort design with concurrent unexposed comparators is the potential for residual or unmeasured confounding because it is unlikely that the data sources will have information on all potential confounders. To address potential confounding and potential misclassification of unexposed status, the SCRI, which automatically adjusts for time-invariant confounders, will be used as a secondary approach where feasible. However, the SCRI is not well suited to study outcomes with gradual onset, long risk intervals, or risk periods that are not well characterized.

A limitation specific to the cohort design with concurrent unexposed comparators is that unvaccinated individuals may become exposed to COVID-19 vaccine at any time during the study; if this situation occurs frequently, the amount of unexposed person-time in the unexposed comparator group will be reduced substantially, which will limit the precision of comparative risk estimates and could potentially lead to substantial imbalances in seasonality between exposed individuals and unexposed individuals, particularly for outcomes with long risk intervals. In primary series analyses, forming separate exposed cohorts by dose number and matching unexposed to exposed at the time of each vaccine will minimize the loss of unexposed person-time due to receipt of vaccine in these individuals between the first and second doses. Additionally, the sensitivity analyses with the historical unexposed comparator cohort for pregnancy and birth outcomes and the SCRI design will not be subject to this limitation. However, it is anticipated that even with separate matching of doses that FU time will be substantially longer in analyses of vaccine-associated enhanced respiratory disease in individuals in the vaccinated cohorts than in the unvaccinated comparator cohorts, since the risk interval is 365 days long. Further, the SCRI design and historical unexposed comparator cohort design are not feasible to be used to study this outcome.

Finally, analyses of third doses of Pfizer-Bio-N-Tech COVID-19 Vaccine (either as an additional dose in a primary series or as a booster dose) may be limited by small numbers of third dose recipients. A large proportion of individuals may be excluded from these analyses if many individuals do not have available information on dose number, as enrollment from the beginning of the authorization of COVID-19 vaccines would be needed to enable dose number identification. The overall number of pregnant women included in the analysis of third doses may be low due to lower COVID-19 vaccine uptake in pregnant women and because pregnant women will be identified by their pregnancy outcomes, which means that

PFIZER CONFIDENTIAL

CT24-WI-GL02-RF02 3.0 Non-Interventional Study Protocol Template For Secondary Data Collection Study 20-May-2021 Page 100 of 120 women will not be identified as pregnant and eligible to be included in the population of pregnant women until months after they give birth or their pregnancy otherwise ends.

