Dose 2 exposed	Record of a second dose in the primary series of Pfizer-BioNTech original monovalent COVID-19 Vaccine	Date of second dose	Record of COVID- 19 vaccine other than Pfizer- BioNTech original monovalent COVID-19 Vaccine before the index date
Dose 3 exposed ^a	For individuals aged 6 months through 4 years: record of a third dose in the primary series of Pfizer-BioNTech original monovalent COVID-19 Vaccine For individuals aged 5 years or older: record of a third dose in the primary series of Pfizer-BioNTech original monovalent COVID-19 Vaccine within 2 months after the second dose	Date of third dose	Record of COVID- 19 vaccine other than Pfizer- BioNTech original monovalent COVID-19 Vaccine before the index date
Dose 1 unexposed	No record of any COVID-19 vaccine as of the index date (i.e., cohort entry) and matched individually to individuals in the dose 1 exposed cohort on time– specific propensity score, age, sex, and state (if feasible, or broader geographic region if not feasible)	Randomly selected date in a period within close temporal proximity to the date of first dose in corresponding exposed individuals (e.g., within the same calendar month)	Record of any COVID-19 vaccine before the index date

Table 1.Cohort definitions for primary series analysis of the general population,
immunocompromised individuals, and individuals with a history of
COVID-19

Cohort	Inclusion criteria	Index date	Exclusion criteria
Dose 2 unexposed	No record of any COVID -19 vaccine as of the index date (i.e., cohort entry) and matched individually to individuals in the dose 2 exposed cohort on time– specific propensity score, age, sex, and state (if feasible, or broader geographic region if not feasible)	Randomly selected date in a period within close temporal proximity to the date of second dose in corresponding exposed individuals (e.g., within the same calendar month)	Record of any COVID-19 vaccine before the index date
Dose 3 unexposed ^a	No record of any COVID-19 vaccine as of the index date (i.e., cohort entry) and matched individually to individuals in the dose 3 exposed cohort on time– specific propensity score, age, sex, and state (if feasible, or broader geographic region if not feasible)	Randomly selected date in a period within close temporal proximity to the date of third dose in corresponding exposed individuals (e.g., within the same calendar month)	Record of any COVID-19 vaccine before the index date

COVID-19 = coronavirus disease 2019.

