8.2.4. Follow-up

Events that can define the start and end of FU are provided in Table 7. Follow-up will end at the earliest of all possible events that define the end of FU.

Safety event of interest	Events defining the start of follow-up	Events defining the end of follow-up ^a
General safety events ^b		
	 Index date (if the risk interval starts on day 0), or One day after the index date (if the risk interval starts on day 1; see Table 8 in Section 8.3.2.1 for outcomespecific risk windows) 	 End of the study period End of data availability Disenrollment from the health plan Death Occurrence of the safety event of interest End of duration of the outcome-specific risk window (maximum of 1 year; see Table 8 in Section 8.3.2.1 for outcome-specific risk windows) Receipt of any brand of COVID-19 vaccine^c
Pregnancy safety outcomes		
Spontaneous abortion	 One day after the index date (if the index date is on or after estimated pregnancy start), or Estimated pregnancy start 	 End of pregnancy 20 weeks of gestation Receipt of and brand of COVID-19 vaccine^c

 Table 7.
 Events defining the start and end of follow-up

Safety event of interest	Events defining the start of follow-up	Events defining the end of follow-up ^a
Stillbirth	 One day after the index date (if the index date is on or after estimated pregnancy start) or Estimated pregnancy start 	 End of pregnancy Receipt of any brand of COVID-19 vaccine^c
Preterm birth	 One day after the index date (if the index date is on or after estimated pregnancy start) or Estimated pregnancy start 	 End of pregnancy 37 weeks of gestation Receipt of any brand of COVID-19 vaccine^c
Major congenital malformations ^d	• Day of birth	 End of study period End of data availability Disenrollment from the health plan Death Diagnosis of major congenital malformation Age 1 year
Small size for gestational age ^d	• Day of birth	• Predefined period shortly after birth (specific period to be defined in the SAP)

Table 7.	Events defining the start and end of follow-up
----------	--

COVID-19 = coronavirus disease 2019; FU = follow-up; SAP = statistical analysis plan.

a. For all analyses, the earliest of the listed events following the index date will mark the end of FU for each outcome. If FU ends due to the occurrence of a particular safety event of interest, FU will continue for all other safety events.

[figure not shown]
b. Safety events of interest are listed in Table 8 in Section 8.3.2.1.

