8.3.2. Outcomes

8.3.2.1. Safety events of interest

Safety events of interest to be assessed in the general population, immunocompromised individuals, individuals with a history of COVID-19, and pregnant women, and their risk

PFIZER CONFIDENTIAL CT24-WI-GL02-RF02 3.0 Non-Interventional Study Protocol Template For Secondary Data Collection Study 20-May-2021

Page 67 of 120

interval definitions, are listed in Table 8. Throughout the protocol, these safety events are referred to as "general safety events."

Safety events of interest include myocarditis/pericarditis and other outcomes being monitored in rapid-cycle analysis of COVID-19 vaccines in the FDA's BEST System (Wong et al., 2021) and the CDC's VSD (Shimabukuro, 2021a), with the addition of vaccine-associated enhanced respiratory disease (Munoz et al., 2021), immune hemolytic anemia, and thromboembolic events with thrombocytopenia. Other safety events of interest may be added as the understanding of the safety profile of Pfizer-BioNTech original monovalent COVID-19 Vaccine evolves and feasibility of their assessment permits in the data sources.

Table 8.General safety events to be assessed in the general population,
immunocompromised individuals, individuals with a history of COVID-
19, and pregnant women

Organ system	Safety event of interest	Risk window (days following receipt of Pfizer-BioNTech original monovalent COVID-19 Vaccine) ^a
Cardiac	Myocarditis/pericarditis	1-21 ^b
	Acute myocardial infarction	1-28
Neurologic	Acute disseminated encephalomyelitis	1-42
	Bell's palsy	1-42
	Convulsions	1-42
	Encephalomyelitis/encephalitis	1-42
	Guillain-Barré syndrome	1-42
	Narcolepsy	1-180
	Transverse myelitis	1-42
Hematologic	Deep vein thrombosis	1-28
	Disseminated intravascular coagulation	1-28
	Immune hemolytic anemia	1-42
	Immune thrombocytopenia	1-42

PFIZER CONFIDENTIAL

CT24-WI-GL02-RF02 3.0 Non-Interventional Study Protocol Template For Secondary Data Collection Study 20-May-2021 Page 68 of 120

Table 8.General safety events to be assessed in the general population,
immunocompromised individuals, individuals with a history of COVID-
19, and pregnant women

Organ system	Safety event of interest	Risk window (days following receipt of Pfizer-BioNTech original monovalent COVID-19 Vaccine) ^a
	Pulmonary embolism	1-28
	Thromboembolic events associated with thrombocytopenia	1-28
	Thrombotic thrombocytopenic purpura	1-28
	Venous thromboembolism	1-28
	Hemorrhagic stroke	1-28
	Ischemic stroke	1-28

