Respiratory	Acute respiratory distress syndrome	1-28
	Vaccine-associated enhanced respiratory disease	1-365
Other system	Anaphylaxis	0-1
	Appendicitis	1-42
	Kawasaki disease	1-42
	Multisystem inflammatory syndrome	1-42

COVID-19 = coronavirus disease 2019.

a. Time interval following vaccination when individuals will be followed for safety events of interest. Day 0 refers to the day of vaccination.

b. Sensitivity analysis will assess alternative risk interval definitions of 1-7 and 1-14 days.

The following pregnancy safety outcomes will be assessed in pregnant women or their infants:

- Spontaneous abortion: spontaneous pregnancy loss before 20 completed weeks gestation, identified using diagnosis codes
- Stillbirth: fetal deaths at or after 20 completed weeks gestation, identified using diagnosis codes

PFIZER CONFIDENTIAL

CT24-WI-GL02-RF02 3.0 Non-Interventional Study Protocol Template For Secondary Data Collection Study 20-May-2021 Page 69 of 120

- Preterm birth: live birth before 37 completed weeks gestation, identified using diagnosis codes
- Major congenital malformations: major congenital malformations will be identified in live-born infants using code lists from the National Birth Defects Prevention Network (NBDPN, 2021a), which defines a major defect as a congenital abnormality that requires medical or surgical treatment, has a serious adverse effect on health and development, or has significant cosmetic impact (NBDPN, 2021b)
- Small size for gestational age: less than 10th percentile of weight for gestational age, identified using diagnosis codes for small size for gestational age

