8.7.2.2. Measures of association

For comparative analyses of general safety events, Cox models or Poisson regression will be used to estimate RRs and 95% CIs within the matched cohorts. For pregnancy outcomes, hazard ratios and 95% CIs will be estimated using Fine-Gray subdistribution proportional hazards models (using gestational age as the time scale) to account for competing risks of other end-of-pregnancy events (e.g., termination, stillbirth) (Fine JP and Gray RJ, 1999).

For comparative analysis of small size for gestational age and major congenital malformations, modified Poisson regression (Zou, 2004) will be used to estimate prevalence ratios and 95% CIs within the matched cohorts.

For the dose 1 comparative risk estimation for general safety events and pregnancy outcomes, when a second dose of vaccine is administered before the risk interval following dose 1 is complete, the risk interval will be truncated at the time of dose 2, and FU after dose 2 will be excluded from the dose 1 risk estimation. In this situation, for the dose 2 comparative risk estimation, the risk interval will start on the date of the second vaccine dose and will extend for the duration of the risk interval for dose 2.

Similarly, for dose 2 comparative risk estimation for general safety events and pregnancy outcomes, when a third dose of vaccine is administered before the risk interval following dose 2 is complete, the risk interval will be truncated at the time of dose 3, and FU after dose 3 will be excluded from the dose 2 estimation. In this situation, for the dose 3 comparative risk estimation, the risk interval will start on the date of the third vaccine dose and will extend for the duration of the risk interval for dose 3.

For comparative analysis of outcomes identified separately in dose 1, dose 2, and dose 3 cohorts, comparative risks will be estimated separately by dose number. If comparative risk estimates are similar for dose 1, dose 2, and dose 3, then data from the dose 1 exposed/dose 1 unexposed cohorts, the dose 2 exposed/dose 2 unexposed cohorts, and the dose 3 exposed/dose 3 unexposed cohorts will be combined to obtain comparative risk estimates associated with at least 1 dose of the vaccine.

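### For the 365-day enhanced respiratory disease window, the protocol predicts unequal follow-up and seasonal imbalance but leaves open a Poisson rate ratio with no control for time

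*Protocol*

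**What the plan says.** **Risk windows (section 8.3.2.1, Table 8).** Two general safety events have windows longer than 42 days: "Vaccine-associated enhanced respiratory disease 1-365" and "Narcolepsy 1-180".

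**Entry.** Calendar time is controlled at the index date. The dose 1 comparator's index date is a "Randomly selected date in a period within close temporal proximity to the date of first dose in corresponding exposed individuals", for example in the same calendar month. The dose 2 and dose 3 cohorts follow the same pattern.

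**End of follow-up (section 8.2.4, Table 7).** Under the table note, "the earliest of the listed events following the index date will mark the end of FU for each outcome". Receipt of any COVID-19 vaccine is one of those events. No rule ends follow-up in the rest of the matched set. Section 8.7.2.2 also truncates the dose 1 interval at dose 2 and the dose 2 interval at dose 3.

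**Model (section 8.7.2.2).** For general safety events, "Cox models or Poisson regression will be used to estimate RRs and 95% CIs within the matched cohorts". No time scale, strata or calendar term is given. The same paragraph does fix a time scale, gestational age, for the pregnancy outcomes.

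**Limitations (section 8.9).** Vaccination of comparators "could potentially lead to substantial imbalances in seasonality between exposed individuals and unexposed individuals, particularly for outcomes with long risk intervals". The protocol anticipates that "FU time will be substantially longer in analyses of vaccine-associated enhanced respiratory disease in individuals in the vaccinated cohorts" than in the unvaccinated comparators. For this outcome it adds that "the SCRI design and historical unexposed comparator cohort design are not feasible to be used to study this outcome".

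**Response.** The only step directed at the imbalance is in section 8.7.1: the length of follow-up in the two cohorts will be output for this outcome.

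**The concern.** Matching on the index month aligns the two groups on calendar time at entry. It does not keep them aligned for a year. When a comparator is vaccinated and leaves, the matched vaccinee stays, and the exposed group accumulates later person-time with no counterpart. A ratio of total events to total person-time then compares an average over one stretch of the calendar with an average over another. If the event rate changes over that stretch, the ratio moves away from the truth even when matching at entry is perfect.

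Section 8.7.2.3.1.1 matches within narrow time periods partly because of the seasonality of circulating infections. For a respiratory outcome followed for 365 days, that protection wears off, and the protocol provides no other design as a check. It presents the resulting imbalance as a limitation of the design, although the choice of analysis can remove most of it.

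**Working it through.** **1. The protocol's own figure.** The protocol gives no number for this outcome or for unequal follow-up. Its precision example (section 8.5) concerns a 21-day window with 1:1 person-time. It reproduces:
- Person-years = 5,000,000 × 2 doses × 21/365.25 = 574,949.
- Expected events at 10 per 100,000 are 57.5 in comparators and 57.5 × 1.4 = 80.5 in vaccinees.
- SE = √(1/57.5 + 1/80.5) = 0.1727.
- Φ(ln(2.5/1.4)/0.1727 − 1.96) = 0.919, against the stated 92%.

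Table 9 covers windows of 21, 28 and 42 days only, so it says nothing about the long ones.

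**2. The mechanism.** Let λ(t) be the event rate t days after index, the same in both groups (true RR = 1). Let S₁(t) and S₀(t) be the shares of exposed and comparators still followed. The crude ratio is

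[ΣS₁λ / ΣS₁] ÷ [ΣS₀λ / ΣS₀].

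It equals 1 if λ is constant or if S₁ and S₀ are proportional. Otherwise it generally does not. Within a stratum of index month and time since index, both groups have the same rate, so the stratified ratio is 1.

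**3. A step change, worked by hand.** Assume comparators leave exponentially with mean 120 days (ΣS₀ = 113.8 days) and the rate changes after day 90.

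| Rate after day 90 | Comparator mean rate | Exposed, all 365 days | Crude ratio | Exposed, stopped at day 21 | Crude ratio |
|---|---|---|---|---|---|
| doubles | 1.446 | (90 + 275×2)/365 = 1.753 | 1.21 | 1.000 | 0.69 |
| halves | 0.777 | (90 + 275×0.5)/365 = 0.623 | 0.80 | 1.000 | 1.29 |

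The day-21 columns represent the dose 1 cohort. Section 6 puts dose 2 at 3 weeks, and section 8.7.2.2 truncates there. The imbalance, and with it the bias, then runs the other way.

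**4. A year of follow-up with boosters.** All inputs are assumed: index months January to June 2021 in equal numbers, 12 months of follow-up in monthly steps, comparators vaccinated at 5, 10 or 20% per month, both groups losing 2% per month, and a December–February rate 2 or 5 times that of other months. Section 6 dates the first booster authorization to 22 September 2021, at 6 months or more after the primary series. Vaccinees at least 6 months past index therefore leave at an extra 0 to 30% per month from October 2021.

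| Extra booster exit per month | Crude ratio | Stratified on time since index only | Also by index month |
|---|---|---|---|
| 0% | 1.019–1.153 | 1.000 | 1.000 |
| 10% | 0.986–1.084 | 0.989–0.997 | 1.000 |
| 20% | 0.926–1.018 | 0.973–0.993 | 1.000 |
| 30% | 0.872–0.985 | 0.953–0.989 | 1.000 |

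The small remainder in the third column arises because booster exit follows the calendar, so survivors at a given time since index are a different mix of index months in the two groups.

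**5. Why the line falls at 42 days.** Assume a sinusoidal yearly rate, vaccinees followed for the whole window, and take the extremes over single entry dates.

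| Amplitude; comparator mean exit | 42 days | 180 days | 365 days |
|---|---|---|---|
| 0.3; 240 days | 1.00 | 0.96–1.05 | 0.93–1.08 |
| 0.5; 120 days | 0.99–1.01 | 0.86–1.18 | 0.82–1.28 |
| 0.8; 60 days | 0.95–1.05 | 0.65–1.82 | 0.64–2.25 |

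These are worst entry dates with no censoring of vaccinees. They show how the problem grows with window length and are not a forecast. At 42 days or less the distortion is at most about 5%.

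**The case against.** The strongest reply is that this is detail for the SAP. Section 8.7 defers detailed methodology there, and its preferred pooling format, risk-set-level data, suggests a time-aligned Cox model. Cox on time since index, already one of the two permitted models, removes most of the bias. The protocol also discloses the imbalance openly.

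Much of that stands, and it limits the point in four ways.

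- A reader might infer that the protocol specifies an unstratified Poisson ratio. It does not; its wording permits one. The confounding depends on that choice.
- A reader might infer that vaccinees are always followed longer and that the RR is pushed upward. Table 7 and section 8.7.2.2 also end exposed follow-up at the next dose. The imbalance reverses in the dose 1 cohort, and booster censoring can turn the sign in the dose 2 cohort.
- A reader might extend the admission to every long window. Section 8.9 states unequal follow-up for enhanced respiratory disease only. Narcolepsy is an inference from its 180-day window, and nothing in the protocol says its rate is seasonal. It too lacks a second design, since section 8.7.3.2 stops at 42 days and section 8.7.3.3 covers only pregnancy and birth outcomes.
- A reader might say no other analysis is planned. Sections 8.7.3.6 and 8.9 allow alternative risk intervals for poorly characterized windows, although within the same cohort design.

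The reply does not dispose of the point. The protocol itself fixes person-level censoring, names Poisson as acceptable, predicts the imbalance, excludes the other two designs for this outcome and answers with a descriptive output. Where it wanted a time scale fixed, for pregnancy outcomes, it fixed one.

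**Conclusion.** The point holds as a conditional one. For enhanced respiratory disease, and for narcolepsy if its recorded rate varies over calendar time, the protocol leaves open an analysis that would confound the RR with calendar time, although the protocol itself predicts the imbalance that causes this. A crude person-time ratio under no effect falls at roughly 0.9 to 1.15 in the year-long illustration; time-aligned estimates are close to 1.00.

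Neither the size nor the direction can be read from the documents. Both depend on dose cohort, comparator uptake, booster censoring and how the event rate moves, and the protocol gives no figures for these. The range shows that the choice of model matters and should not be quoted as the expected bias. The general safety events with windows of 42 days or less are not materially affected.

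**What to change.** In section 8.7.2.2, for risk windows longer than 42 days:

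- Require a time-aligned analysis: either Cox regression on time since index, stratified by matched set or index month, or Poisson regression with calendar-time terms.
- State that a crude person-time Poisson ratio will not be used for these outcomes.
- Optionally offer matched-pair censoring as an alternative or sensitivity analysis, ending both members' follow-up when either one's ends.

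The cost is a sentence or two of text and slightly more analysis work; no new data are needed. Matched-set stratification and pair censoring give up some late exposed person-time that has no comparator, and pair censoring shifts the weight of a 365-day question towards early follow-up. Stratifying by index month, or using calendar-time terms, loses less.
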